**Table 1. Study Activities (Continued)**

- h. Chest x-ray includes posterior-anterior (PA) and lateral views. Obtain chest x-ray for subjects with TB risk factors as identified by the TB risk factor questionnaire or for subjects living in areas endemic for TB or for subjects with positive PPD or QuantiFERON-TB Gold. Subjects can have a chest x-ray anytime during the study as warranted based on the opinion of the Investigator.
- i. PPD skin test is to be read 48 to 72 hours after placement.
- j. Dipstick urinalysis will be completed by the sites at all required visits. A microscopic analysis will be performed by the central laboratory, in the event the dipstick results show protein, ketones or blood greater than negative or glucose greater than normal.
- k. Serum pregnancy test will be performed on all women of childbearing potential at Screening and at Week 52/ET. Urine pregnancy test will be performed locally at every visit for all women of childbearing potential. If any urine pregnancy test is positive, a serum pregnancy test will be performed by the central laboratory.  
If required by country regulatory authorities, monthly pregnancy tests will be performed throughout the study.
- l. Subjects will be tested for the presence of the hepatitis B Virus (HBV) and hepatitis C Virus (HCV) at Screening. A positive result for the hepatitis B surface antigen (HBs Ag) or hepatitis C (HCV RNA detectable in any subject with anti-HCV Ab) will be exclusionary. For subjects who are negative for HBs Ag but are positive for core antibodies (HBc Ab), HBV DNA PCR will be performed and any result that meets or exceeds detection sensitivity will be exclusionary.
- m. For all subjects, a PK sample will be collected at Week 2, within 1 to 3 hours after dosing, if possible. At Week 4, Week 8, Week 12, Week 16, Week 20, Week 28, Week 36, Week 44 and Week 52/ET, a blood sample for PK will be collected at any time during the visit, and preferably within 1 to 8 hours after the last dose. Patients can take the dose on visit days at their regular schedule and not necessarily at the clinic. The date and accurate time of the PK sample collection and the last ABT-494 dose will be recorded in the CRF to the nearest minute.
- n. Stool sample will be collected at each time point indicated. For the visit that endoscopy will be conducted, stool sample should be collected prior to endoscopy.
- o. A stool sample will be collected for fecal calprotectin analysis at each time point indicated. Subjects will be asked to provide a stool sample at the visit, if possible, or subjects will be sent home with instructions and stool sample supplies (supplies will be provided).
- p. Subject is mandated to begin corticosteroid taper at Week 2.
- q. Collection of SAEs begins the day the subject signs the informed consent.
- r. Only if subject provides written consent to collect the pharmacogenetic sample; if the informed consent form is not signed, no pharmacogenetic sample can be collected. The sample is preferred to be collected at BL.

**Table 1. Study Activities (Continued)**

- s. Only if subject provides written consent to collect the serum biomarkers and mRNA samples; if the informed consent form is not signed, no serum biomarkers and mRNA can be collected.
- t. Only if subject provides written consent to collect biopsy samples for gene expression analysis; if the informed consent form is not signed, no biopsy for gene expression can be collected. Biopsies will be obtained at baseline and as the Week 12/16 endoscopy, based on the colonoscopy assignment for Week 12 or 16.
- u. Optional tests, only if determined by the investigator and based on the medical assessment.
- v. Laboratory tests performed during the Screening period can be repeated in case the abnormalities are considered to be transient by the investigator.

### **5.3.1.1                    Study Procedures**

The study procedures outlined in [Table 1](#) are discussed in detail in this section, with the exception of drug concentration measurements (discussed in Section [5.3.2](#)), pharmacogenetic and pharmacodynamic biomarkers, serologic markers, mRNA and gene expression samples (discussed in Section [5.3.1.2](#), Section [5.3.1.3](#), Section [5.3.1.4](#), Section [5.3.1.5](#), and Section [5.3.1.6](#), respectively), and the collection of adverse event (AE) information (discussed in Section [6.1.4](#)). All study data will be recorded in source documents and on the appropriate eCRFs.

#### **Informed Consent**

At the Screening Visit, the subject will sign and date a study specific, Independent Ethics Committee (IEC)/Independent Review Board (IRB) approved, Informed Consent Form before any study procedures are performed or any medications are withheld from the subject in order to participate in this study. A separate informed consent will be required for each subject in order to participate in the optional pharmacogenetic analysis, serological biomarker, mRNA analysis and gene expression. Details regarding how informed consent will be obtained and documented are provided in Section [9.3](#).

#### **Inclusion/Exclusion Criteria**

Subjects will be evaluated to ensure they meet all inclusion criteria and have none of the exclusion criteria at both Screening and Baseline Visits.

#### **Medical and Surgical History**

A complete medical and surgical history, including CD-onset date, history of CD medication use, and history of alcohol and tobacco use will be obtained from each subject at the Screening Visit. An updated medical history will be obtained prior to study drug administration at Baseline, to ensure the subject is still eligible for enrollment, and updated as necessary.

Prior corticosteroid, azathioprine, 6-MP, MTX and aminosalicylate use will be asked. If subjects have/had ever been treated with these medications, the duration of therapy, maximum dose, reason for use and reason(s) for termination of treatment will be recorded in subjects' source document and in appropriated eCRF. The details of dates of administration and dosages will be also recorded within the past 90 days.

A detailed anti-TNF therapy history will be recorded, this includes names of anti-TNF used, duration of therapy, doses, reason (s) for use and reason(s) for termination of treatment with these products (e.g., Inadequate Response, Intolerance, primary failure, secondary failure) must be documented in the subjects' source documents and in appropriated eCRF.

A detailed medical history with respect to Inadequate Response and/or Intolerance to an immunomodulator or anti-TNF agent must be documented in the subjects source documents. A detailed medical history with respect to TB exposure will be documented. This information will include BCG vaccination, cohabitation with individuals who have had TB, and residence or work in TB endemic locations.

### **Physical Examination**

A physical examination including evaluation of extra intestinal manifestations will be performed at the designated study visits as specified in [Table 1](#).

A full physical examination will be performed at Screening, Baseline, Week 16 and Week 52/ET Visit and must include an assessment of extra-intestinal manifestations (EIMs) and a count of the number of cutaneous fistulas. Symptom-based physical examinations will be performed at all other visits must include a count of the number of cutaneous fistulas.

The physical examination at the Baseline Visit will serve as the Baseline physical examination for the entire study. A count of the number of cutaneous fistulas draining upon gentle compression must be performed during each physical exam. Fistulas will be classified as abdominal or perianal/anal. Physical examination abnormalities noted by the

Investigator at Baseline prior to the first dose of study drug (including fistulas and fissures) will be recorded in the subject's medical history. Abnormalities noted after the Baseline Visit and first dose of study drug will be evaluated and documented by the Investigator as to whether or not these are adverse events. All findings whether related to an adverse event or part of each subject's medical history will be captured on the appropriate eCRF page.

A symptom-directed physical examination will be performed when necessary.

### **Vital Signs**

Vital sign determinations of systolic and diastolic blood pressure in sitting position, pulse rate, respiratory rate, body weight, and body temperature will be obtained at each visit. Blood pressure, pulse rate and respiratory rate should be performed before blood draws are performed. Height will be measured at the Screening Visit only (with shoes off). All measurements will be recorded in metric units where applicable.

### **Chest X-Ray (CXR)**

A chest x-ray (posterior-anterior and lateral views) will be obtained for all subjects with TB risk factors as identified by the TB risk factor questionnaire ([Appendix G](#)) or for subjects living in areas endemic for TB or for subjects with a positive PPD or QuantiFERON-TB Gold. The Investigator may obtain a Baseline chest x-ray if clinically indicated for a specific subject. Subjects can have a chest x-ray anytime during the study as warranted based on the opinion of the Investigator.

The Principal Investigator will indicate the clinical significance of any findings and will sign and date the report.

### **Electrocardiogram (ECG)**

A resting 12-lead ECG will be performed at the designated study visits as specified in [Table 1](#). A qualified physician will interpret the clinical significance of any abnormal finding, sign, and date each ECG. Any clinically significant findings will be documented

in the source documents and later transcribed on to the appropriate eCRF. Each signed original ECG will be monitored by the responsible CRA and kept with subject's source documents onsite.

For subjects with a normal ECG taken within 90 days of Screening, a repeat ECG at Screening will not be required, provided all protocol required documentation is available. If there are other findings that are clinically significant, the Principal Investigator must contact the SDP before enrolling the subject.

Subjects can have a repeat ECG at any time during the study as warranted based on the opinion of the Investigator.

### **TB Screening**

The TB screening tests are diagnostic test results to be interpreted in the context of the subject's epidemiology, history, exam findings, etc. and it is the responsibility of the investigator to determine if a subject has active or latent tuberculosis.

For all subjects, evidence of increased risk for TB will be assessed by a questionnaire ([Appendix G](#)) and testing (PPD skin test or QuantiFERON-TB Gold [or equivalent]). Subjects with a negative QuantiFERON®-TB Gold test OR negative PPD TB skin test AND no evidence of increased TB risk based on the questionnaire may be enrolled. Subjects with a positive QuantiFERON-TB Gold test OR a positive PPD skin test (defined as 5 mm of induration or greater) OR at increased risk of TB based on questionnaire/geography should have a chest x-ray. Subjects with evidence of latent TB may be enrolled after at least 2 weeks of prophylactic treatment per local guidelines.

If a subject had a negative PPD test or QuantiFERON-TB Gold test (or interferon-gamma release assay-IGRA-equivalent such as T-SPOT TB test) test within 90 days prior to Screening and all protocol required documentation is available, the test does not need to be repeated, provided nothing has changed in the subject's medical history to warrant a repeat test. These cases must be discussed with the AbbVie Study Designated Physician.

Subjects should be screened for TB using either PPD or IGRA. In the event both a PPD test and an IGRA test are performed, if either one is positive the subject will be considered to be positive. If the IGRA test is indeterminate, the site should repeat the test. If the second IGRA test is also indeterminate, the subject is considered to be positive.

Subjects with evidence of latent TB may be enrolled after at least 2 weeks of prophylactic treatment per local guidelines.

Subjects with evidence of active TB infection are excluded.

The results of the TB test(s) will be retained at the site as the original source documentation.

**QuantiFERON-TB Gold Test (or IGRA Equivalent such as T-SPOT TB Test)**

QuantiFERON-TB Gold test (or IGRA equivalent such as T-SPOT TB test) will be performed at Screening. The analyses will be performed by a certified laboratory.

**OR**

**TB Skin Test**

A PPD skin test (alternatively, also known as a TB Skin Test or Mantoux test) will be performed at Screening according to standard clinical practice. The TB Skin Test should be read by a licensed healthcare professional between 48 and 72 hours after administration. A subject who does not return within 72 hours will need to be rescheduled for another skin test. The reaction will be measured in millimeters (mm) of induration and induration equal to or greater than 5 mm is considered a positive reaction. The absence of induration will be recorded as "0 mm" not "negative."

**Pregnancy Tests**

A serum pregnancy test will be performed at the Screening and Week 52/ET Visit on all female subjects of childbearing potential.

Women of childbearing potential includes all women who are not surgically sterile (both ovaries removed or uterus removed) or post-menopausal (defined as no menses for at least one year, without an alternate reason for amenorrhea).

At the Baseline Visit, subjects of childbearing potential will have a urine pregnancy test performed locally by designated study personnel. If any urine pregnancy test is positive, a serum pregnancy test will be performed by the central laboratory. If the serum pregnancy test is positive, dosing must be stopped and the subject must be discontinued from the study.

A lactating or pregnant female will not be eligible for participation or continuation in this study.

All women of childbearing potential will have a repeat urine pregnancy test at every Study Visit performed locally by designated study personnel.

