- At least one 4-week induction with Adalimumab: one 160 mg SC dose (or 80 mg SC dose in approved countries) followed by one 80 mg SC dose (or 40 mg SC dose in approved countries) followed by one 40 mg dose at least 2 weeks apart
- At least one 4-week induction with Certolizumab pegol: 400 mg SC, 2 doses at least 2 weeks apart OR
  - Recurrence of symptoms during scheduled maintenance dosing following prior clinical benefit (discontinuation despite clinical benefit does not qualify) OR
  - History of intolerance of at least one TNF antagonist (including, but not limited to infusion-related reaction, demyelination, congestive heart failure and infection)

7. Subject has a negative tuberculosis (TB) Screening Assessment. If the subject has evidence of a latent TB infection, the subject must initiate and complete a minimum of 2 weeks (or per local guidelines, whichever is longer) of an ongoing TB prophylaxis or have documented completion of a full course of anti-TB prophylaxis, prior to Baseline.

8. A negative serum pregnancy test for all female subjects at the Screening Visit and a negative urine pregnancy test for all female subjects of childbearing potential at baseline prior to the first dose of study drug.

---

9. If female, subject must be either postmenopausal, OR permanently surgically sterile OR for women of childbearing potential practicing at least one protocol-specified method of birth control (refer to Section 5.2.4), that is effective from Study Day 1 through at least 30 days after the last dose of study drug.
10. Male subjects who are sexually active with female partner(s) of childbearing potential must agree from Study Day 1 through 30 days after the last dose of study drug to practice the protocol-specified contraception (refer to Section 5.2.4).
11. Subject must be able and willing to give written informed consent and to comply with the requirements of this study protocol.
12. Subject is judged to be in otherwise good health as determined by the Principal Investigator based upon the results of medical history, laboratory profile, physical examination and a 12-lead electrocardiogram (ECG) performed during Screening.

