## 5.2.4 Contraceptive Recommendations

### Contraception Recommendation for Females

A woman who is postmenopausal or permanently surgically sterile (bilateral oophorectomy, bilateral salpingectomy or hysterectomy) is not considered to be a woman of childbearing potential and is not required to follow contraception recommendations.

Postmenopausal is defined as:

- Age  $\geq$  55 years with no menses for 12 or more months without an alternative medical cause; or
- Age  $<$  55 years with no menses for 12 or more months without an alternative medical cause AND an FSH level  $>$  40 mIU/mL.

A woman who does not meet the definition of postmenopausal or permanently surgically sterile is considered a woman of childbearing potential and is required to practice at least one of the following highly effective method of birth control, on Study Day 1 (or earlier) through at least 30 days after the last dose of study drug.

- Combined (estrogen and progestogen containing) hormonal contraception (oral, intravaginal, transdermal) associated with the inhibition of ovulation, initiated at least 1 month prior to Study Day 1.
- Progestogen-only hormonal contraception (oral, injectable, implantable) associated with inhibition of ovulation, initiated at least 1 month prior to Study Day 1.
- Bilateral tubal ligation.
- Vasectomized partner(s), provided the vasectomized partner has received medical assessment of the surgical success and is the sole sexual partner of the WOCBP trial participant.
- Intrauterine device (IUD).
- Intrauterine hormone-releasing system (IUS).
- True abstinence: Refraining from heterosexual intercourse when this is in line with the preferred and usual lifestyle of the subject (periodic abstinence)

---

[e.g., calendar, ovulation, symptothermal, post-ovulation methods] and withdrawal are not acceptable)

If required per local practices, male or female condom with or without spermicide OR cap, diaphragm or sponge with spermicide should be used in addition to one of the highly effective birth control methods listed above (excluding true abstinence).

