### **5.3 Efficacy and Safety Assessments/Variables**

Study procedures will be performed as summarized in Section 5.3.1.1. All subjects must meet the study selection criteria outlined in Section 5.2.1 and Section 5.2.2 in order to be randomized in to the study.

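### Protocol 5.2.4 and 5.3.1.1 define childbearing potential differently, so some women under 55 who must use contraception fall outside pregnancy testing from Baseline onward

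*Protocol*

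**What the plan says.** **Contraception (Protocol 5.2.4, to which inclusion criterion 9 refers).** A woman aged 55 or over is postmenopausal after 12 months without menses and with no other medical cause. Below 55 the rule adds a hormone condition: "years with no menses for 12 or more months without an alternative medical cause AND an FSH level" above 40 mIU/mL. Everyone else falls to the protective default: "A woman who does not meet the definition of postmenopausal or permanently surgically sterile is considered a woman of childbearing potential". Such a woman "is required to practice at least one of the following highly effective method of birth control".

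**Testing (Protocol 5.3.1.1, Pregnancy Tests).** This subsection gives its own definition. Women of childbearing potential are those neither surgically sterile nor "post-menopausal (defined as no menses for at least one year, without an alternate reason for amenorrhea". Neither age nor FSH appears. The Baseline urine test and the Week 52/early-termination serum test are limited to women of childbearing potential, as are the visit tests: "All women of childbearing potential will have a repeat urine pregnancy test at every Study Visit performed locally by designated study personnel".

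**Links between the two.** Section 5.3 points sites to the procedure text: "Study procedures will be performed as summarized in Section 5.3.1.1". Table 1 footnote k uses the term childbearing potential without defining it. FSH is in neither Table 1 nor the laboratory list in Table 2.

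**Screening.** Inclusion criterion 8 asks for "A negative serum pregnancy test for all female subjects at the Screening Visit", whereas footnote k says "Serum pregnancy test will be performed on all women of childbearing potential at Screening and at Week 52/ET", and 5.3.1.1 sets the same limit.

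**The concern.** The protocol pairs two safeguards for women who could conceive: effective contraception and regular testing. With two definitions, the group covered by the first is wider than the group covered by the second. Women in the difference rely on contraception alone during up to 52 weeks of dosing.

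Pregnancy requires withdrawal (5.4.1 and 6.1.6), and under 5.3.1.1 a positive serum test stops dosing. Scheduled testing is how the protocol finds a pregnancy, so without it that safeguard may act late. These women are already amenorrheic and would have no missed period to alert them. Sites can also reach different answers for the same patient, depending on which section they apply.

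**Working it through.** No sample-size, power or error-rate figure is involved, so the check is a case comparison followed by a count of visits.

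**1. Case comparison.** Take women who are not surgically sterile and have had at least 12 months without menses and no other explanation. Eligible ages are 18 to 75 (inclusion criterion 1), so all three rows can enrol.

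| Case | Under 5.2.4 | Under 5.3.1.1 | Result |
|---|---|---|---|
| Age 55 or over | Postmenopausal | Postmenopausal | Agree |
| Under 55, FSH > 40 mIU/mL | Postmenopausal | Postmenopausal | Agree |
| Under 55, FSH ≤ 40 or not measured | Childbearing potential; contraception required | Postmenopausal; no tests from Baseline on | **Conflict** |

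Because FSH is not a scheduled test, an unmeasured value in the third row is foreseeable.

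**2. Does Screening close the gap?** Only at Screening. Criterion 8 requires a serum test there from every female, but its Baseline urine test is again limited to women of childbearing potential. The gap therefore starts at Baseline.

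**3. Size of the gap.** The pregnancy-test row of Table 1 gives these visits from Baseline:

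- Baseline and Weeks 2, 4, 8, 12, 16, 20, 28, 36, 44 and 52: 11 visits.
- Adding the 30-day follow-up: 11 + 1 = 12 time points.
- Intervals between on-treatment tests: 2, 2, 4, 4, 4, 4, 8, 8, 8 and 8 weeks. Sum: 2 + 2 + (4 × 4) + (4 × 8) = 52 weeks. Maximum: 8 weeks.

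| Woman in the third row | Scheduled tests, Baseline to Week 52 | Longest gap between scheduled tests on treatment |
|---|---|---|
| Classed by 5.2.4 | 11 | 8 weeks |
| Classed by 5.3.1.1 | 0 | No scheduled test in 52 weeks |

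**4. Surgical sterility.** Section 5.2.4 counts bilateral salpingectomy as sterility; 5.3.1.1 lists only removal of both ovaries or of the uterus. This mismatch runs the other way: the woman is tested although contraception is not required. It creates no safety gap.

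**The case against.** The strongest reply is that the sections can be read together. The 5.3.1.1 sentence says what the group includes, which need not be exhaustive. Section 5.2.4 classes the affected woman as of childbearing potential, and 5.3.1.1 tests all such women. Sites reach 5.2.4 first through criterion 9, footnote k adds no narrower rule, and Section 5.3 says where procedures are summarized, not which definition prevails. A site could indeed carry over her 5.2.4 status and test her. But the natural reading of 5.3.1.1 is that it defines the group to be tested, and nothing else in the protocol reconciles the two definitions.

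The following also stands:

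- **The group is narrow.** Amenorrhea with another explanation, such as a hormonal contraceptive, does not count as postmenopausal under 5.3.1.1, so those women are tested.
- **Other safeguards remain.** These are the Screening serum test, mandatory contraception, reporting within 1 working day once the site is aware of a pregnancy, and withdrawal. Only the first is a test, and it precedes dosing.
- **Timing limits what a correction recovers.** Amendment 5 is dated 07 November 2016. The induction analysis follows the last subject's Week 16, and the extension SAP dates that database lock to December 2016. Even with a lock on 31 December, the last randomization was 16 weeks earlier, in about mid-September. Changed Screening or Baseline wording would reach no new subject, but remaining visits, including those in the extension, would still benefit.
- **The Screening mismatch is separate and secondary.** Criterion 8 already requires the test, so it leaves no safety gap. Restricting criterion 8 instead would also remove the contradiction.

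**Conclusion.** The concern holds. For a woman under 55, not surgically sterile, with at least a year of unexplained amenorrhea and FSH at or below 40 mIU/mL or not measured, the protocol requires contraception but, as 5.3.1.1 is written, schedules no pregnancy test from Baseline onward.

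The size, 0 rather than 11 scheduled tests from Baseline to Week 52, assumes that the site applies 5.3.1.1 literally, that she completes the full course, and that no national rule for monthly testing covers her. The number of such women cannot be derived from the documents and is probably small. This is a consistency defect in patient safety that should be corrected; it touches no efficacy endpoint or analysis. The conclusion does not depend on the Screening mismatch.

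**What to change.** - **Main change.** Delete the definition in 5.3.1.1, refer there to 5.2.4, and have Table 1 footnote k cite 5.2.4. Every woman required to use contraception is then tested, and one under 55 without a documented FSH above 40 mIU/mL is treated as of childbearing potential.
- **Direction.** Do not move the 5.3.1.1 definition into 5.2.4; that would remove the contraception requirement from these women.
- **Screening.** State in 5.3.1.1 and footnote k that the Screening serum test is for all females, as criterion 8 already requires.
- **FSH.** Scheduling it at Screening is optional. Without a result, 5.2.4 defaults to contraception and, after this change, to testing.

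**Cost.** Amendment wording in two places, a few extra local urine tests, and one Week 52/early-termination serum test per reclassified woman. No new analyte is needed. One side effect is that women sterile by bilateral salpingectomy would no longer be scheduled for tests after Screening, in line with their status under 5.2.4.
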